8.2 Safety Laboratory Assessment

Samples for safety laboratory assessments (biochemistry, lipids, hematology, coagulation, and urinalysis) will be collected at:

- Screening/Baseline, Week 2, Week 4, Week 6, and Week 12 (Flare-up Component).

Values and changes from baseline will be summarized at each scheduled visit with descriptive statistics. Mean values (+/- standard error) will be plotted over time during the Flare-up Component for triglycerides, cholesterol, alanine aminotransferase, aspartate aminotransferase, amylase, and lipase. Note that results obtained locally rather than from the central laboratory will not be used to calculate change from baseline and will be excluded from these summaries.

Potentially clinically significant (PCS) values at baseline and new-onset PCS values post-baseline will be summarized with counts and percentages of subjects or flare-ups as appropriate. New-onset PCS values are defined as values that were not PCS at baseline and were PCS post-baseline. Note that results obtained locally will be included in these summaries. PCS values are defined in [Table 4](#).

Table 4. Potentially Clinically Significant Safety Laboratory Values

	PCS Low	PCS High
Biochemistry		
Aspartate aminotransferase	N/A	3 x ULN
Alanine aminotransferase	N/A	3 x ULN
Amylase	N/A	3 x ULN
Lipase, pancreatic	N/A	3 x ULN
Bilirubin	N/A	>2 mg/dL
Thyroxine	<4.0 mcg/dL	>13.0 mcg/dL
Lipids		
Cholesterol	N/A	>300 mg/dL
Triglycerides	N/A	>400 mg/dL
Hematology		
Leukocytes	<2.8 x 10 ⁹ /L	>16.0 x 10 ⁹ /L
Hemoglobin (females)	<9.5 g/dL	>17.5 g/dL
Hemoglobin (males)	<11.5 g/dL	>19.0 g/dL
Hematocrit (females)	<32%	>54%
Hematocrit (males)	<37%	>60%
Platelets	<75 x 10 ⁹ /L	>700 x 10 ⁹ /L

A listing will be provided for all subjects with PCS lipase values that will include all lipase results during the study along with associated palovarotene and glucocorticoid dosing data (dose and start and stop dates).

8.3 Vital Signs

Vital signs (blood pressure, heart rate, respiratory rate, and temperature) will be collected at:

- Screening/Baseline, Week 2, Week 4, Week 6, and Week 12 (Flare-up Component).

Values and changes from baseline will be summarized at each scheduled visit with descriptive statistics. Mean values (+/- standard error) will be plotted over time during the Flare-up Component for blood pressure and heart rate.

Potentially clinically significant (PCS) values at baseline and new-onset PCS values post-baseline will be summarized with counts and percentages of subjects or flare-ups as appropriate. New-onset PCS values are defined as values that were not PCS at baseline and were PCS post-baseline. PCS values are defined in [Table 5](#).

Table 5. Potentially Clinically Significant Vital Sign Values

	PCS Low	PCS High
Systolic blood pressure	<86 mmHg or a decrease of ≥ 25 mmHg from baseline	>180 mmHg or an increase of ≥ 25 mmHg from baseline
Diastolic blood pressure	<48 mmHg or a decrease of ≥ 20 mmHg from baseline	>110 mmHg or an increase of ≥ 20 mmHg from baseline
Heart rate	<45 bpm or a decrease of ≥ 20 bpm from baseline	(1) >105 bpm AND an increase of ≥ 20 bpm from baseline (2) >125 bpm

mmHg=millimeters of mercury, bpm=beats per minute.

8.4 Body Weight

Body weight will be collected at:

- Screening/Baseline, Week 2, Week 4, Week 6, and Week 12 (Flare-up Component).

Values and changes from baseline will be summarized at each scheduled visit with descriptive statistics. Mean values (+/- standard error) will be plotted over time during the Flare-up Component.

8.5 Knee and Hand/Wrist Radiograph

Subjects under the age of 18 years at the time of enrollment into Study PVO-1A-202 with open epiphyseal growth plates will undergo knee and hand/wrist radiographs (AP view) at:

- Screening/Baseline and Week 12 (Flare-up Component).

Knee and hand/wrist radiographs will be performed remotely (eg, at a local medical facility) for subjects who are unable or unwilling to attend site visits. Once a subject has achieved 100% skeletal maturity (as confirmed by radiography), knee and hand/wrist radiographs will no longer be required. The incidence of abnormalities may be summarized with counts and percentages of subjects.

8.6 Linear Growth Assessment

A linear growth assessment will be performed for subjects under the age of 18 years at the time of enrollment into Study PVO-1A-202 with open epiphyseal growth plates at:

- Screening/Baseline and Week 12 (Flare-up Component).

Height will be measured at Study Month 12 (Follow-up Component) and Screening/Baseline (Flare-up Component).

Based on work by Chumlea (1994)³, knee height can be used to predict total height (stature) for children who are mobility-impaired. Separate equations were established for White and for Black children by gender, as follows:

- White boys: predicted stature = $40.54 + (2.22 \times \text{knee height})$
- Black boys: predicted stature = $39.60 + (2.18 \times \text{knee height})$
- White girls: predicted stature = $43.21 + (2.15 \times \text{knee height})$
- Black girls: predicted stature = $46.59 + (2.02 \times \text{knee height})$

When race is not reported as White or Black, the calculation for the White boy/girl will be used.

Values and changes from baseline will be summarized for height, knee to heel length, and predicted stature at each scheduled visit with descriptive statistics. Values for height and knee to heel length may be plotted over time with the actual palovarotene dose taken at each visit identified.

8.7 Electrocardiogram

A 12-lead electrocardiogram (ECG) will be performed at:

- Screening/Baseline and Week 6 (Flare-up Component).

Values and changes from baseline will be summarized for continuous ECG parameters at each scheduled visit with descriptive statistics.

Abnormal ECG categories will be assigned based on raw findings as shown in [Table 6](#).

Table 6. Abnormal Electrocardiogram Categories

Abnormal ECG Category	Raw Findings
Rhythm	
 * Atrial premature complexes * Ventricular premature complexes * Sinus arrhythmia * Sinus tachycardia
Conduction	
 * Nonspecific intraventricular conduction delay * Right bundle branch block * Incomplete right bundle branch block * Left posterior fascicular block * Left bundle branch block * Incomplete left bundle branch block
Morphology/Chamber enlargement	
 * Left ventricular hypertrophy * Left ventricular hypertrophy with repolarization abnormality
Axis deviation	
 * Right axis deviation * Left axis deviation
Myocardial infarction	
 * Pathologic Q waves * Acute ST elevation MI * Acute non-ST elevation MI
ST Segment/T Waves/U Waves	
 * Early repolarization * Nonspecific ST and T wave abnormality * Nonspecific ST elevation * Nonspecific U wave abnormalities
Miscellaneous	
 * Long QT interval * Short PR interval

Overall interpretation and abnormal ECG categories will be summarized at each scheduled visit with counts and percentages of flare-ups. New-onset ECG abnormalities are defined as abnormalities that did not exist at baseline. New-onset ECG abnormalities will be summarized counts and percentages of flare-ups.

Incidence of QTc >450 msec, QTc >500 msec, or change from baseline in QTc >60 msec will be summarized with counts and percentages of flare-ups.

Potentially clinically significant (PCS) values at baseline and new-onset PCS values post-baseline will be summarized with counts and percentages of flare-ups. New-onset PCS values are defined as values that were not PCS at baseline and were PCS post-baseline. PCS values are defined in [Table 7](#).

Table 7. Potentially Clinical Significant Electrocardiogram Values

	PCS Low	PCS High
PR interval	N/A	>200 msec or an increase of ≥ 20 msec
QRS interval	N/A	>100 msec or an increase of ≥ 10 msec
QT interval, QTcF, QTcB	N/A	>500 msec or an increase of ≥ 60 msec

msec = millisecond, QTcF = rate-corrected QT interval using Fridericia's formula (QT interval divided by the cube root of the RR interval), QTcB = rate-corrected QT interval using Bazett's formula (QT interval divided by the square root of the RR interval)

8.8 Physical Examination

A comprehensive physical examination will be performed at:

- Screening/Baseline, Week 6, and Week 12 (Flare-up Component).

Physical examination results will be summarized at each scheduled visit by body system with counts and percentages of flare-ups.

8.9 Columbia-Suicide Severity Rating Scale

Suicidal ideation and behavior will be assessed using the Columbia-Suicide Severity Rating Scale (C-SSRS) at:

- Screening/Baseline, Week 2, Week 4, Week 6, Week 9, and Week 12 (Flare-up Component).

Data listings will be provided for (1) all C-SSRS results; and (2) for subjects reporting any type 4 or type 5 suicidal ideations.

9 References

Appendices

Appendix 1. PROMIS T-Score Conversions

The following conversion tables allow a user to convert Global Physical Health, Global Mental Health, and Total scores into T-scores. T-score distributions are standardized such that a 50 represents the average (mean) for the US general population, and the standard deviation around that mean is 10 points. A high score always represents more of the concept being measured. Thus, a subject who has a T-score of 60 is one standard deviation better (more healthy) than the general population.

Adult Global Physical Health		
Raw Score	T-Score	Standard Error
4	16.2	4.8
5	19.9	4.7
6	23.5	4.5
7	26.7	4.3
8	29.6	4.2
9	32.4	4.2
10	34.9	4.1
11	37.4	4.1
12	39.8	4.1
13	42.3	4.2
14	44.9	4.3
15	47.7	4.4
16	50.8	4.6
17	54.1	4.7
18	57.7	4.9
19	61.9	5.2
20	67.7	5.9

Adult Global Mental Health		
Raw Score	T-Score	Standard Error
4	21.2	4.6
5	25.1	4.1
6	28.4	3.9
7	31.3	3.7
8	33.8	3.7
9	36.3	3.7
10	38.8	3.6
11	41.1	3.6
12	43.5	3.6
13	45.8	3.6
14	48.3	3.7
15	50.8	3.7
16	53.3	3.7
17	56.0	3.8
18	59.0	3.9
19	62.5	4.2
20	67.6	5.3

Pediatric Self-Completed Total		
Raw Score	T-Score	Standard Error
7	16.0	3.4
8	17.1	3.6
9	18.3	3.7
10	19.7	3.8
11	21.2	3.8
12	22.8	3.7
13	24.4	3.6
14	26.1	3.6

Pediatric Proxy-Completed Total		
Raw Score	T-Score	Standard Error
7	14.7	2.9
8	15.3	3.1
9	16.0	3.2
10	16.9	3.4
11	18.1	3.6
12	19.4	3.7
13	21.0	3.8
14	22.7	3.8

Pediatric Self-Completed Total			Pediatric Proxy-Completed Total		
Raw Score	T-Score	Standard Error	Raw Score	T-Score	Standard Error
15	27.6	3.5	15	24.4	3.7
16	29.2	3.5	16	26.1	3.7
17	30.8	3.5	17	27.7	3.7
18	32.4	3.6	18	29.4	3.8
19	34.0	3.6	19	31.2	3.8
20	35.6	3.6	20	32.9	3.8
21	37.2	3.6	21	34.6	3.8
22	38.8	3.6	22	36.2	3.8
23	40.4	3.6	23	37.9	3.9
24	42.1	3.7	24	39.7	4.0
25	43.9	3.7	25	41.7	4.0
26	45.7	3.6	26	43.6	3.9
27	47.5	3.6	27	45.4	3.8
28	49.2	3.6	28	47.3	3.9
29	51.1	3.7	29	49.3	4.1
30	53.3	3.9	30	51.8	4.4
31	55.7	4.2	31	54.5	4.7
32	58.3	4.5	32	57.3	5.0
33	61.1	4.9	33	60.2	5.4
34	64.2	5.4	34	63.2	6.0
35	67.5	6.1	35	66.1	6.5

Statistical Analysis Plan

A Phase 2, Open-Label Extension, Efficacy and Safety Study of a RAR γ -Specific Agonist (Palovarotene) in the Treatment of Preosseous Flare-ups in Subjects with Fibrodysplasia Ossificans Progressiva (FOP)

Study Number: PVO-1A-202 Part B

Original Protocol: 04 June 2014
Amendment 1: 30 September 2014
Amendment 2: 22 June 2015
Amendment 3: 10 March 2016

Statistical Analysis Plan Version: 1.0
Statistical Analysis Plan Date: 23 October 2018

NRS	numeric rating scales
PCS	potentially clinically significant
PROMIS	Patient-Reported Outcomes Measurement Information System
RAR γ	retinoic acid receptor gamma
ROM	range of motion
SAE	serious adverse event
SAP	statistical analysis plan
ULN	upper limit of normal
US	Ultrasound
WBCT	whole body CT

1 Introduction

This Statistical Analysis Plan (SAP) describes the analyses to be performed for Study PVO-1A-202 Part B based on Amendment 3 of the protocol dated 10 March 2016 and the France-specific Amendment 1 of the protocol for Study PVO-1A-204, dated 07 September 2016. Data collected for Study PVO-1A-202 Part B and Study PVO-1A-204 will be combined for the analyses. For the purposes of this SAP, “Study PVO-1A-202 Part B” (or simply “Part B”) represents data from both studies.

The analyses performed for Study PVO-1A-202 Parts A and C are described in separate SAPs.

2 Overview

2.1 Study Objectives

2.1.1 Primary Objective

The primary objective is:

- To evaluate the safety and efficacy of different palovarotene dosing regimens in subjects with FOP. Efficacy will be assessed based on the ability of palovarotene to prevent the formation of new heterotopic ossification (HO) as assessed by low-dose computed tomography (CT) scan (or plain radiographs for subjects unable to undergo CT scan).

2.1.2 Secondary Objectives

- To evaluate the effect of palovarotene to prevent HO as assessed by low-dose, whole body computed tomography (WBCT) scan, excluding head.
- To evaluate the effect of palovarotene on active range of motion (ROM) at the flare-up site as assessed by goniometer.
- To evaluate the effect of palovarotene on ROM as assessed by the Cumulative Analogue Joint Involvement Scale (CAJIS) for FOP.
- To evaluate the effect of palovarotene by the subject and Investigator global assessment of movement at the flare-up site.
- To evaluate the effect of palovarotene on physical function using age-appropriate forms of the FOP Physical Function Questionnaire (PFQ).
- To evaluate the effect of palovarotene on physical and mental health using age-appropriate forms of the Patient Reported Outcomes Measurement Information System (PROMIS) Global Health Scale.
- To evaluate the effect of palovarotene on pain and swelling associated with the flare-up using numeric rating scales (NRS) or the Facial Pain Scale-Revised (FPS-R) in subjects under 8 years of age.
- To evaluate the effect of palovarotene on the use of assistive devices and adaptations for daily living by FOP subjects.
- To evaluate the effects of palovarotene on soft tissue swelling and cartilage formation at the flare-up site as assessed by magnetic resonance imaging (MRI); or the effect of

palovarotene on soft tissue swelling as assessed by ultrasound (US) in subjects unable to undergo MRI.

- To evaluate bone, cartilage, angiogenesis, and inflammation biomarkers and explore correlations between changes from baseline in biomarkers and clinical efficacy.
- To evaluate the pharmacokinetics of palovarotene during the first treated flare-up.
- To evaluate the ability of different dosing regimens of palovarotene to prevent new flare-ups.
- To evaluate the long-term safety and efficacy of prior palovarotene treatment at the original flare-up site in Study PVO-1A-201; efficacy will be based on the amount of new HO formed at the original flare-up site as assessed by low-dose CT scan (or plain radiographs in subjects unable to undergo CT scan) in the Pediatric Cohort or low-dose whole body CT scan, excluding head, in the Adult Cohort.

2.2 Study Population

A total of approximately 60 subjects will be enrolled in Part B including approximately 40 subjects who completed Study PVO-1A-201 and up to 20 new Adult Cohort subjects. The Adult Cohort will include subjects with at least 90% skeletal maturity, regardless of age; the Pediatric Cohort will include subjects with less than 90% skeletal maturity, regardless of age. Any Pediatric Cohort subject who achieves $\geq 90\%$ skeletal maturity during Part B may be considered for enrollment into the Adult Cohort at the discretion of the Investigator.

Flare based analyses will include the treatment groups: PVO 20/10 mg, Prior Non-Flare-up/PVO 20/10 mg, and Combined PVO 20/10 mg (=PVO 20/10 mg + Prior Non-Flare-up/PVO 20/10 mg groups). PVO 20/10 mg is defined as flare-ups that did not have prior non-flare-up treatment. Prior Non-Flare-up/PVO 20/10 mg is defined as flare-ups that were treated with Non-Flare-up 5 mg treatment prior to the start of the flare-up treatment. It is important to mention that the flare-up analyses is based on flare-ups, thus subjects may be included in both treatment groups, depending on when non-flare-up dosing began.

WBCT analyses are based on the PVO Non-Flare-up/PVO 20/10 mg treatment group and will include the following subsets: Treated Flare-ups, Under/Untreated Flare-ups, No Flare-ups, and Combined Treated/No Flare-ups.

Only subjects with Non-Flare-up treatment are imaged using WBCT, thus only the PVO Non-Flare-Up/PVO 20/10 mg treatment group is present. This treatment group is subset into 3 different treatment groups, depending on whether or not the subjects had treated, untreated or no flares during the duration between the baseline and Month 12 WBCT scans. Treated Flare-ups are defined as subjects who received non-flare-up/flare-up regimen for all flare-ups. Under/Untreated Flare-ups are defined as subjects who did not receive palovarotene dosing for all flare-ups. No flare-ups are defined as subjects who received the non-flare-up regimen and did not report any flare-ups.

Safety treatment groups include the PVO 20/10 mg and Non-Flare-up 5 mg groups.

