$AUC_{0-24(ss)}$	Area under the concentration versus time curve over the 24-hour dosing interval; calculated using linear trapezoid rule.
$C_{max(ss)}$	Maximum or peak measured plasma concentration at steady-state.
$C_{min(ss)}$	Minimum or trough measured plasma concentration at steady-state.
$T_{max(ss)}$	Time of maximum or peak measured plasma concentration at steady-state, obtained by inspection.
CL/F	Clearance defined as: $Dose/AUC_{0-24(ss)}$.
λ_z	Terminal rate constant
$t_{1/2z}$	Apparent terminal elimination half-life; calculated as $\ln(2)/\lambda_z$. The number of data points included in the regression will be determined by visual inspection, but a minimum of three data points in the terminal phase, excluding C_{max} , will be required to estimate λ_z .

9 Changes from Protocol

For the purposes of clarity and consistency of nomenclature, the Flare-up Rate Population described in the protocol was renamed as the Non-Flare Treated Population.

The initial secondary objective listed in Section 2.1.2 was not included in Amendment 3 of the protocol for Study PVO-1A-202 Part B or Amendment 1 of the protocol for Study PVO-1A-204.

The protocol describes the primary comparison of outcomes to be from data collected from the NHS and Phase 2 study. These comparisons will be performed in a future analysis and the analysis described here will instead focus on comparisons solely from Study PVO-1A-202 Part B between treatment groups of PVO 20/10 mg and Prior Non-Flare-up/PVO 20/10 mg, for flare based analyses; and treatment groups of treated, untreated, or no-flares, for WBCT based analyses.

10 References

3. D'Agostino, RB., Jr., Tutorial in Biostatistics: Propensity Score Methods for Bias Reduction in the Comparison of a Treatment to a Non-Randomized Control Group. *Statistics in Medicine*, 1998, 17, 2265-2281.

Appendices

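### Part B SAP: the WBCT comparison is between post-baseline flare-up subsets of one treated group, so it is confounded by flare-up count and estimates no drug effect

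*SAP*

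**What the plan says.** Section 2.1.2 of the Part B SAP states the objective as a drug effect: "To evaluate the effect of palovarotene to prevent HO as assessed by low-dose, whole body computed tomography (WBCT) scan, excluding head". Section 2.2 explains that WBCT is done only in subjects on non-flare-up treatment, so there is one treatment group. It then splits that group: "This treatment group is subset into 3 different treatment groups, depending on whether or not the subjects had treated, untreated or no flares", judged over the interval between the baseline and Month 12 scans. The output "will include the following subsets: Treated Flare-ups, Under/Untreated Flare-ups, No Flare-ups, and Combined Treated/No Flare-ups". The definitions are:

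- Treated: "Treated Flare-ups are defined as subjects who received non-flare-up/flare-up regimen for all flare-ups".
- Under/Untreated: "Under/Untreated Flare-ups are defined as subjects who did not receive palovarotene dosing for all flare-ups".
- No Flare-ups: "No flare-ups are defined as subjects who received the non-flare-up regimen and did not report any flare-ups".

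Section 9 defers the comparison with the natural history study (NHS) and the Phase 2 data to a future analysis. It says the present analysis will focus instead on comparisons within Part B, between "treatment groups of treated, untreated, or no-flares, for WBCT based analyses". Section 3.1 plans no modelling and no covariate adjustment, and Section 2.5 confirms that there is no randomisation.

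**The concern.** All subsets are on the same non-flare-up regimen, so none of them is a control. What separates them is what happened between the two scans whose difference is the outcome. Flare-ups are the events that the trial treats as leading to HO: its title calls them preosseous, and the primary endpoint in Section 6.1 is new HO after a flare-up. No Flare-ups therefore selects subjects without the event that drives the outcome. If one untreated flare-up is enough for Under/Untreated, the chance of landing there is 1 − q^k for k flare-ups each treated with probability q, which rises with k. Section 2.1.2 also lists prevention of new flare-ups as an objective, so the grouping conditions on another outcome of treatment.

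At stake is the reading of the WBCT table. With the subsets labelled treatment groups and named as the comparison, a difference in flare-up frequency can be taken for an effect of treating flare-ups.

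**Working it through.** The plan gives no sample-size figure, flare-up rate or treatment probability for this analysis, so there is nothing to reproduce. The check asks what the subsets show when the drug does nothing.

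**Assumptions (not in the documents).** Flare-ups per subject over 12 months have mean L = 1 to 2. Each is treated with probability q = 0.7 to 0.9, independently of frequency and severity. Each adds one unit of new HO whether treated or not. Background HO is zero at first. Under/Untreated means not every flare-up was treated.

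**Poisson counts.** Treated and untreated flare-ups are independent, with means b = Lq and a = L(1 − q). Let g(x) = x/(1 − e^(−x)), the mean of a Poisson count given at least one event. Expected new HO is 0 for No Flare-ups, g(b) for Treated, b + g(a) for Under/Untreated, and b for Combined Treated/No Flare-ups.

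Example, L = 1, q = 0.7: b = 0.7, a = 0.3, g(0.7) = 1.39, g(0.3) = 1.16. Treated is 1.39, Under/Untreated 0.70 + 1.16 = 1.86, Combined 0.70.

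**Gamma(1,1) frailty on the rate.** Counts are geometric. With r = Lq/(1 + L), Combined is r/(1 − r) and Treated is 1/(1 − r). The Combined share of subjects is P = 1/[(1 + L)(1 − r)], so Under/Untreated is (L − P × Combined)/(1 − P).

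Example, L = 2, q = 0.9: r = 0.6, Combined 1.5, Treated 2.5, P = 0.833, Under/Untreated (2 − 1.25)/0.167 = 4.5.

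| Counts | L | q | Treated | Under/Untreated | Combined | Treated ÷ Under | Combined ÷ Under |
|---|---|---|---|---|---|---|---|
| Poisson | 1 | 0.7 | 1.39 | 1.86 | 0.70 | 0.75 | 0.38 |
| Poisson | 1 | 0.9 | 1.52 | 1.95 | 0.90 | 0.78 | 0.46 |
| Poisson | 2 | 0.7 | 1.86 | 2.73 | 1.40 | 0.68 | 0.51 |
| Poisson | 2 | 0.9 | 2.16 | 2.90 | 1.80 | 0.74 | 0.62 |
| Frailty | 1 | 0.7 | 1.54 | 2.54 | 0.54 | 0.61 | 0.21 |
| Frailty | 1 | 0.9 | 1.82 | 2.82 | 0.82 | 0.65 | 0.29 |
| Frailty | 2 | 0.7 | 1.88 | 3.88 | 0.88 | 0.48 | 0.23 |
| Frailty | 2 | 0.9 | 2.50 | 4.50 | 1.50 | 0.56 | 0.33 |

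The spurious reduction for Combined is 38% to 62% (Poisson) or 67% to 79% (frailty). For Treated alone it is 22% to 32% or 35% to 52%.

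**Background HO.** Adding one flare-up's worth to every subject under Poisson gives, for Combined, (1 + 0.70)/(1 + 1.86) = 0.59 at L = 1, q = 0.7 and (1 + 1.80)/(1 + 2.90) = 0.72 at L = 2, q = 0.9. The reduction falls to about 28% to 41%. For Treated it falls to about 15% to 23%.

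**Treatment not independent of the flare-up.** This was simulated with 1,000,000 subjects per setting, gamma frailty, lognormal HO per flare-up and background 0.5. If severe flare-ups are treated more often, Treated ÷ Under is 0.72 to 0.99. If frequent flarers are treated more often, it reverses to 1.09 to 1.55. Combined ÷ Under stayed below 1 in all 12 settings (0.31 to 0.82).

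**The other reading of Under/Untreated (none treated).** The Poisson mean for that subset becomes g(a). At L = 1, q = 0.7, Treated ÷ Untreated is 1.39/1.16 = 1.20; at L = 2, q = 0.9, it is 2.16/1.10, about 1.95. A null drug now looks harmful. Combined can also exceed Untreated: 1.40 against 1.33 at L = 2, q = 0.7.

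**Treated against No Flare-ups.** With no background HO this is 1.39 against 0 at L = 1, q = 0.7, which counts against treatment by construction.

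**Population.** Section 4.6 draws the WBCT Population from the Flare-up Population, whose members took flare-up treatment. No Flare-ups could then hold only subjects whose treated flare-up fell outside the baseline to Month 12 window. Requiring at least one treated flare-up within the window, L = 1, q = 0.7 gives Treated g(b) = 1.39 against Under/Untreated g(b) + g(a) = 2.55, a ratio of 0.55.

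**The case against.** Much of the remedy is already in the plan. Section 6.3 says efficacy data for non-flare-up treatment will generally be presented in total for the WBCT Population. Section 6.3.1 asks only for descriptive statistics by subset, with no test or decision rule, and omits the Combined subset. Section 9 defers the natural history comparison rather than dropping it, and discloses the change. The primary endpoint in Section 6.1 is not touched. No passage explicitly sets Combined against Under/Untreated, and the zero-flare-up subjects who pull Combined down would mostly be excluded by Section 4.6.

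All of this stands, and it limits the harm. It does not remove the fault: Section 2.2 still calls the subsets treatment groups and lists the Combined one, and Section 9 still makes the contrast between subsets the focus of the WBCT analysis.

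A reader might also infer that an inert drug would necessarily look beneficial, by two thirds or more. The documents do not support that. The 67% to 79% figure needs gamma frailty and zero background HO, neither of which is in the plan. The direction differs by pair, by how flare-ups come to be treated, and by how Under/Untreated is read.

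**Conclusion.** Wrong as written. Sections 2.2 and 9 present post-baseline strata of one treated group as treatment groups and make them the WBCT comparison, without adjustment. Differences between the strata are confounded by flare-up count and do not estimate the effect named in Section 2.1.2. That conclusion needs only that flare-ups contribute to HO.

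The size rests on assumed rates. With 1 to 2 flare-ups a year, treatment probability 0.7 to 0.9, treatment independent of frequency, no background HO and the not-every-flare-up reading, Combined shows a spurious reduction of about 38% to 62% (Poisson) or 67% to 79% (frailty) against Under/Untreated. Treated alone shows about 22% to 52% across the two models. The Treated contrast reverses if frequent flarers are preferentially treated or if the definition means none treated, and Treated against No Flare-ups is biased against treatment. Because the summaries are secondary and descriptive, the harm is a misleading comparison, not an inflated type I error.

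**What to change.** - In Sections 2.2 and 9, stop calling the subsets treatment groups and stop naming them as the WBCT comparison.
- State that the main WBCT result is the change in all subjects on the non-flare-up regimen with baseline and Month 12 scans, as one group. This fits the in-total presentation in Section 6.3. State also that the effect question rests on the deferred natural history comparison.
- Delete the Combined Treated/No Flare-ups subset from Section 2.2; Section 6.3.1 already omits it.
- Keep the other subsets as descriptive strata and show flare-up counts beside the HO results. Define Under/Untreated unambiguously, so that a subject with some but not all flare-ups treated has a stated place.
- Reconcile Section 4.6, and the matching line in Section 5.1, with the No Flare-ups subset, which the current population definition would leave nearly empty.

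The cost is SAP wording and one changed table, with no new data. The downside is that Part B alone then gives no between-group WBCT contrast.
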